#### Patient diary endpoints:

##### Bowel habits

- Mean movement frequency per day
- Maximum movement frequency per day
- Maximum single consistency score

#### Description of Bowel Habits:

Bowel habit ((frequency and consistency of patient's stools) data will be collected using patient diary cards as per schedule of protocol. Bowel movement consistency will be recorded for each patient in five categories –

Document: \\ieedc-vnasc01\BIOSdata\GSK\BRL25000\PPD Biostatistics\Documentation\SAP  
 Author: PPD Version Number: V1.0  
 Version Date: 18JUL2022

Template No.: CS\_TP\_BS016 Revision 6

Reference: CS\_WI\_BS005

Effective Date: 02Dec2019

CC1 - This section contained Clinical Outcome Assessment data collection questionnaires or indices, which are protected by copyright.  
[REDACTED] = 1, [REDACTED] = 2, [REDACTED]  
CC1 - This section contained Clinical Outcome Assessment data collection questionnaires or indices, which are protected by copyright.  
[REDACTED] = 3, [REDACTED] = 4, [REDACTED] = 5.  
CC1 - This section contained Clinical Outcome Assessment data collection questionnaires or indices, which are protected by copyright.  
[REDACTED]

Summary measures of bowel habit movement frequency and consistency are defined as –

- Mean movement frequency per day: this measures the mean number of bowel movements experienced by each patient during the study
- Maximum movement frequency per day: this measures the maximum number of bowel movements experienced in a day for each patient
- Maximum single consistency score: this measures the maximum consistency score for each patient at any time during the study

Clinical Recurrence of Disease - Reappearance of signs/symptoms for those participants who were clinically cured or improved at the end of therapy.

### 15.1.1. ANALYSIS OF SECONDARY ENDPOINT

#### 15.1.1.1. Clinical Response

Frequency and proportion of early, primary, and secondary clinical response will be presented along with 95% CI using exact binomial method

Secondary clinical response statistical analysis will be performed based on as collected data. The following summaries will be generated for early, primary, and secondary clinical response by overall and indication.

- Early clinical response at on-therapy (OT) visit
- Primary clinical response at end of therapy (EOT) visit
- Secondary clinical response at follow-up (FU) visit

Clinical recurrence of disease at follow-up will be summarized with frequency and percentage by overall and indication.

#### 15.1.1.2. Incidence of protocol- defined diarrhoea (PDD).

No intercurrent event is defined for this endpoint. The data will be analyzed as collected.

Document: \\ieedc-vnasc01\BIOSdata\GSK\BRL25000\PPD Biostatistics\Documentation\SAP  
Author: PPD

Version Number: V1.0  
Version Date: 18JUL2022

Template No.: CS\_TP\_BS016 Revision 6

Reference: CS\_WI\_BS005

Effective Date: 02Dec2019

Frequency and percentage of subjects with incidence of protocol- defined diarrhoea (PDD) will be presented along with 95% CI using exact method (refer SAS code APPENDIX 3)

The following summaries will be generated for incidence of protocol- defined diarrhoea (PDD) by overall and indication.

- Incidence of protocol-defined diarrhoea (PDD)
- Incidence of protocol defined diarrhoea (PDD) over time

Figure for incidence of protocol defined diarrhoea (PDD) over time will also be displayed by overall and indication.

The statistical analysis for incidence of protocol- defined diarrhoea (PDD) will be based on as collected data.

#### 15.1.1.3. Patient diary endpoints

Bowel habits-

The following summaries will be generated for patient summary measures of bowel habit movement by overall and indication.

- Summary and descriptive statistics for patient bowel habit summary measure - mean movement frequency per day
- Summary and descriptive statistics for patient bowel habit summary measure - maximum movement frequency per day
- Summary and descriptive statistics for patient bowel habit summary measure - maximum consistency score

Subject listing of bowel movement by indication will be presented using ITT population.

## 16. SAFETY ENDPOINTS

All analysis for safety endpoints will be based on the Intent to treat Analysis Set.

### 16.1. ADVERSE EVENTS

The primary safety endpoint is the number of subjects reporting at least one treatment emergent

Document:	\\ieedc-vnasc01\BIOSdata\GSK\BRL25000\PPD	\\Biostatistics\Documentation\SAP
Author:	PPD	Version Number: V1.0 Version Date: 18JUL2022

Template No.: CS\_TP\_BS016 Revision 6

Reference: CS\_WI\_BS005

Effective Date: 02Dec2019

adverse event (TEAE).

A TEAE duration is defined as an AE which has its onset date during the treatment period + lag time of 1 day.

Adverse Events (AEs) will be coded using MedDRA version 24.1. TEAE's and SAE's will be summarized. All AE's will be listed.

#### 16.1.1. TEAES: PRIMARY SAFETY ENDPOINT

AEs occurring from when a subject sign informed consent to when a subject exits the study will be accounted for in the reporting. AEs occurring pre-treatment, treatment emergent adverse event (on-treatment) and post-treatment periods will be summarized and listed for the ITT population. A treatment -emergent adverse event is defined as any adverse event that develops after initiation of the study treatments or any adverse event already present that worsens following exposure to study treatment.

The primary safety endpoint will be summarized with counts and percentage of subjects reporting any TEAEs and subjects with at least one or any TEAE with corresponding 95% CI using exact binomial method

The following summaries will be generated for adverse events:

- Adverse event overview by period
- Adverse event overview by period for acute otitis media (AOM)
- Adverse event overview by period for acute bacterial rhinosinusitis (ABRS)
- Adverse event overview by period for community acquired bacterial pneumonia (CABP)
- Treatment emergent adverse events by system organ class, preferred term, overall and indication
- Adverse events by system organ class, preferred term, overall and indication - post-treatment
- Common ( $\geq 1\%$ ) treatment emergent adverse events by preferred term, overall and indication
- Common ( $\geq 1\%$ ) adverse events by preferred term, overall and indication - post-treatment

AEs and TEAEs will be sorted by descending order of system organ class (SOC) and total frequency of preferred term (PT) within each system organ class (SOC).

AEs and TEAEs related to study drug will be presented in decreasing order of preferred term (PT). Subjects listing of adverse events by indication (TEAE and post-treatment period) will be produced.

#### 16.1.1.1. Severity

Severity is classified as mild, moderate, and severe. An AE with missing severity will be classified as 'Unknown'.

Subjects who experience the same event several times, with different intensities, will only be counted with the maximum intensity.

The following tables will be generated to summarize the severity of adverse event

- Treatment emergent adverse events by system organ class, preferred term, maximum severity, overall and indication
- Adverse events by system organ class, preferred term, maximum severity, overall and indication -post treatment

Sorting order will be presented same as section 16.1.1.

#### 16.1.1.2. Relationship to Study Medication

Summary for drug-related treatment emergent adverse events by preferred term, overall and indication will be presented.

### 16.1.2. TEAES LEADING TO PERMANENT DISCONTINUATION OF STUDY MEDICATION OR WITHDRAWAL STUDY

Treatment emergent adverse events leading to permanent discontinuation of study medication or withdrawal from study by system organ class, preferred term, overall and indication will be displayed.

Adverse events leading to withdrawal from study will also be presented by system organ class, preferred term, overall and indication.

Sorting order will be presented same as section 16.1.1.

Subject listing of treatment emergent adverse events leading to permanent discontinuation of study medication or withdrawal from study will also be generated.

---

Document: \\ieedc-vnasc01\BIOSdata\GSK\BRL25000\PPD\Biostatistics\Documentation\SAP  
Author: PPD

Version Number: V1.0  
Version Date: 18JUL2022

Template No.: CS\_TP\_BS016 Revision 6

Reference: CS\_WI\_BS005

Effective Date: 02Dec2019

### **16.1.3. SERIOUS ADVERSE EVENTS**

The following summaries will be presented for serious adverse events:

- Treatment emergent serious adverse events by system organ class, preferred term, overall and indication
- Serious adverse events by system organ class, preferred term, overall and indication - post-treatment
- Treatment emergent serious adverse events by system organ class and preferred term, maximum severity, overall and indication
- Serious adverse events by system organ class, preferred term, maximum severity, overall and indication -post treatment
- Drug-related treatment emergent serious adverse events by preferred term, overall and indication

Sorting order will be presented same as section 16.1.1.

The following serious adverse event listings will be produced:

- Listing of reasons for considering as a serious adverse event by indication- pre-treatment
- Listing of fatal and non-fatal serious adverse events (TEAE and post-treatment period)
- Listing of reasons for considering as a serious adverse event by indication (TEAE and post-treatment period)

### **16.1.4. ADVERSE EVENTS LEADING TO DEATH**

Subject listing will be generated for adverse event leading to death.

### **16.1.5. CARDIOVASCULAR EVENTS**

The following AE's/SAE's will be classified as Cardiovascular events:

- Myocardial infarction/unstable angina
- Congestive heart failure
- Arrhythmias
- Valvulopathy
- Pulmonary hypertension

---

Document:	\\ieedc-vnasc01\BIOSdata\GSK\BRL25000\PPD	\\Biostatistics\Documentation\SAP
Author:	PPD	Version Number: V1.0 Version Date: 18JUL2022

Template No.: CS\_TP\_BS016 Revision 6

Reference: CS\_WI\_BS005

Effective Date: 02Dec2019

- Cerebrovascular events/stroke and transient ischemic attack
- Peripheral arterial thromboembolism
- Deep venous thrombosis/pulmonary embolism
- Revascularization

Subject listing will be generated for all cardiovascular events recorded in the study.

## 16.2. DEATHS

Subject listing will be generated for any death that happens during the study.

## 16.3. LABORATORY EVALUATIONS

Laboratory parameters assessed for the study are listed below:

Table 5:

Assessments	Parameters		
Hematology	Platelet Count RBC Count Hemoglobin Hematocrit	RBC Indices: MCV MCH %Reticulocytes	WBC count with Differential: Neutrophils Lymphocytes Monocytes Eosinophils Basophils
Clinical Chemistry	Plasma creatinine	Aspartate Aminotransferase (AST) Alanine Aminotransferase (ALT)	Total and direct bilirubin
Radiography	Chest X ray to be performed for patients presumed to a diagnosis of CABP. X ray of nasal/paranasal sinus to be performed for patients presumed to have ABRS (both only for reference, as per investigators discretion)		

- Clinical laboratory evaluations include hematology, clinical chemistry, A list of laboratory assessments is mentioned in Table 5 which will be used for statistical analysis.
- Descriptive statistics (n, mean, standard deviation (SD), median, minimum value

Document: \\ieedc-vnasc01\BIOSdata\GSK\BRL25000\PPD\Biostatistics\Documentation\SAP  
 Author: PPD

Version Number: V1.0  
 Version Date: 18JUL2022

Template No.: CS\_TP\_BS016 Revision 6

Reference: CS\_WI\_BS005

Effective Date: 02Dec2019

(min), and maximum value (max)) will be presented for quantitative measurements of laboratory parameters by overall and indication. Frequency and percentage will be displayed for qualitative measurements of laboratory parameters by overall and indication.

- Subjects listing of baseline laboratory parameters by indication will also be generated.

## 16.4. ECG EVALUATIONS

ECG assessment will not be performed for this study.

## 16.5. VITAL SIGNS

The following Vital Signs measurements will be reported for this study:

- Respiratory Rate (breaths/min)
- Temperature (° C)
- Pulse rate
- Weight (kg)
- Height

Actual vital signs results, change from baseline values and percentage change from baseline will be summarized for each analysis visit.

Subjects listing of vital signs parameters by indication will also be generated.

## 16.6. OTHER SAFETY ASSESSMENTS

Summary for visits impacted by COVID-19 pandemic will be presented by overall and indication.

Subject listing of Covid-19 pandemic study impact (TEAE and post-treatment period) will be displayed.

Subject listing of local examination by indication will be generated.

Document: \\ieedc-vnasc01\BIOSdata\GSK\BRL25000\PPD  
Author: PPD

Biostatistics\Documentation\SAP

Version Number: V1.0

Version Date: 18JUL2022

Template No.: CS\_TP\_BS016 Revision 6

Reference: CS\_WI\_BS005

Effective Date: 02Dec2019

Subject listing will be generated for pregnancy.

## 17. DATA NOT SUMMARIZED OR PRESENTED

Not applicable

## APPENDIX 1. PROGRAMMING CONVENTIONS FOR OUTPUTS

### IQVIA OUTPUT CONVENTIONS

Outputs will be presented according to IQVIA Global Biostatistics Standard Output Conventions

#### DATES & TIMES

Depending on data available, dates and times will take the format DDMMMYYYY; times will take the format HH:MM; combined dates and times will take the format DDMMMYYYY/HH:MM. Time will be based on a 24 hour clock.

#### SPELLING FORMAT

English UK, including for MedDRA where British English is used.

#### LISTINGS

All listings will be ordered by the following (unless otherwise indicated in the template):

- Subject ID
- Date and time (where applicable)

#### PRESENTATION OF TREATMENT GROUPS

For outputs, treatment groups will be represented as follows:

Treatment Group
Augmentin (ES) – 600

#### DESCRIPTIVE STATISTICS

If the original data has N decimal places, then the summary statistics will have the following decimal places:

Document:	\\ieedc-vnasc01\BIOSdata\GSK\BRL25000	PPD	Biostatistics\Documentation\SAP
Author:	PPD		Version Number: V1.0
			Version Date: 18JUL2022
Template No.:	CS_TP_BS016	Revision 6	Reference: CS_WI_BS005

Effective Date: 02Dec2019

- Minimum and maximum: N;
- Mean, median, lower and upper bounds of two-sided 95% CI: N + 1;
- SD and SE: N + 2

## PERCENTAGES

Percentages will be reported to one decimal place. Rounding will be applied, except for percentages < 0.1 but > 0.0 which will be presented as '< 0.1' and percentages < 100.0 but > 99.9 which will be presented as '>99.9'.

Where counts are zero, no percentages will appear in the output.

---

Document:	\\ieedc-vnasc01\BIOSdata\GSK\BRL25000\PPD	\\Biostatistics\Documentation\SAP
Author:	PPD	Version Number: V1.0
		Version Date: 18JUL2022
Template No.:	CS_TP_BS016 Revision 6	Reference: CS_WI_BS005

Effective Date: 02Dec2019

## APPENDIX 2. PARTIAL DATE CONVENTIONS

Date Imputation Rule for adverse events and concomitant medication for assigning the event in particular period:

Missing day in a start date, e.g. --JUN2021, set to the first of the month, 01JUN2021.

Missing month in a start date, e.g., 15--2006, set to January, 15JAN2021.

Missing day in a stop date, e.g. --APR2021, set to the last of the month, 30APR2021.

Missing month in a stop date, e.g., 23--2006, set to December, 23DEC2021.

If both day and month are missing, e.g. ----2021, apply both rules giving 01JAN2021 for a partial start date, or 31DEC2021 for a partial stop date

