^j Local examination refers to ear, nose/paranasal sinus or chest examination depending upon the primary diagnosis ie, AOM, ABRS or CABP

^k Includes assessment of disease at baseline and evaluation of clinical improvement or deterioration at other visits during study, as per Investigator’s discretion.

^l Includes baseline signs and symptoms (other than disease under study).

^m The parent/legal guardian should record the AEs, dosing information, diarrhoea related information in the Dairy Card through the treatment period and until EOT. Patient Diary cards will be appropriately translated for all languages required based on sites participating in the trial.

ⁿ All AEs will be collected from the signing of the ICF until the follow-up visit at the time points specified.

^o The secondary clinical response evaluation will be performed at scheduled FU visit only for participants who were treatment successes at the EOT. This is unlike participants with disease recurrence post EOT, whose secondary clinical response evaluation would have already taken place at interim visit, at the time of recurrence.

^p Incidence of protocol-defined diarrhoea will be assessed (as a secondary endpoint) at EOT (Day 12 to 14), scheduled FU visit (Days 22 to 28) and interim visit, if any.

^q Not required for the participants who were withdrawn from the study intervention due to worsening, or no improvement, or requirement of additional antibiotics during OT visit (Day 3 to 5).

*In case first dose can be given on Day 0 (after laboratory test result availability), the same will be considered as Day 1.

**Rationale for range: Days 3 to 5; 12 to 14; 15 to 21, and 22 to 28: Basis previous GSK studies. Day 15 to 21 is to cover interim period between EOT and FU to factor any disease recurrence. Refer to Section 5.4 for the details of the evaluation to be performed at each visit.

*** Participants with disease recurrence following the EOT visit (Day 12 to 14), but prior to the scheduled FU visit (Day 22 to 28) will be required to visit the study site twice - once during interim visit at time of recurrence (Day 15 to 21) and again at scheduled FU visit (Day 22 to 28). At interim visit all the evaluations which are to be performed at scheduled FU visit, including primary and secondary endpoint assessments will be performed. However, at scheduled FU visit (Day 22 to 28), all evaluations conducted at interim visit will be repeated, except secondary clinical response.

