### Treatment Period for Adverse Events:

#### Pre-Treatment AE's:

An AE will be said to be pre-treatment AE if  
AE Start Date < Study Treatment Start Date

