#### Treatment Emergent Adverse Event:

An AE will be defined as Treatment emergent adverse event (TEAE) if the AE start date is on or after treatment start date & on or before treatment stop date +1

Study Treatment Start Date ≤ AE Start Date ≤ Study Treatment Stop Date +1

If the last dose of study drug is missing and the AE start date is on or after the first dose of study drug, then the AE will be considered as TEAE

If the AE start date is missing or partial then the AE will be considered TEAE unless there is evidence to the contrary (e.g. month/year of onset date is present and is earlier than the month/year of first dose of study medication).

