**On-Treatment Period:**

If Con-med start date < study treatment start date (or Con-med start date is missing) and con-med stop date  $\geq$  study treatment start date (or Con-med start date is missing), or

If study treatment start date  $\leq$  Con-med start date  $\leq$  study treatment stop date+1.

If the study treatment stop date is missing and the con-med start date is on or after the study treatment start date, then the con-med will be on-treatment.

If the con-med start or stop date is missing or partial, then the con-med will be considered on-treatment unless there is evidence to the contrary (e.g. month/year of con-med stop date is present and is before the month/year of study treatment start date).

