## 12. CONCOMITANT MEDICATIONS

Pre-treatment medication is defined as any medication that started and stopped prior to the first dose of study drug.

Concomitant medication is defined as any medication which started before the first dose of study drug AND was ongoing at the time of the first dose of study drug, or started on or after the date of first dose of study drug.

Medications with partially or completely missing start and/or stop dates will be handled as described in Section 6.4.

All medications will be coded using the World Health Organization (WHO) Drug Global dictionary version B3 September 2021.

Concomitant medications will be summarized using anatomical therapeutic class (ATC) level 1 and ingredient by overall and indication for pre-, on and post- treatment based on the ITT analysis population. A subject having more than one medication within the same ATC Level 1 or ingredient will be counted only once for that ATC Level 1 or ingredient. Subjects listings will be provided for concomitant medications.

Concomitant medications will be sorted in descending order of total incidence across Augmentin ES treatment group for the ATC level 1 and in descending order of total incidence for the ingredient within each ATC level 1 class.

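### SAP Appendix 2 and SAP 6.4 can put the same adverse event with a partial start date in different periods, and nothing says which rule governs adverse events

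*SAP*

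**What the plan says.** The SAP has two rules for an AE whose start date is incomplete.

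- **SAP Appendix 2** presents itself as a "Date Imputation Rule for adverse events and concomitant medication for assigning the event in particular period". Its first rule is: "Missing day in a start date, e.g. --JUN2021, set to the first of the month, 01JUN2021". A missing month becomes January. For a date with only the year: "If both day and month are missing, e.g. ----2021, apply both rules giving 01JAN2021 for a partial start date".
- **SAP 6.4, treatment-emergent AEs**: "If the AE start date is missing or partial then the AE will be considered TEAE unless there is evidence to the contrary". The one example of such evidence is a recorded onset month and year earlier than the month and year of first dose.

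SAP 6.4 also defines a pre-treatment AE by the inequality "AE Start Date < Study Treatment Start Date". A TEAE starts between first dose and the day after last dose.

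For medications, SAP 6.4 has the same default: when a date is missing or partial, "then the con-med will be considered on-treatment unless there is evidence to the contrary". SAP 12 then says: "Medications with partially or completely missing start and/or stop dates will be handled as described in Section 6.4". The AE text in SAP 6.4, 16.1 and 16.1.1 has no such pointer, and neither 6.4 nor Appendix 2 refers to the other. SAP 7.3 says that missing data are not imputed and makes no exception for dates.

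**The concern.** The TEAE flag defines the primary endpoint, the proportion of children with at least one TEAE. Treatment lasts 10 days, so first dose and onset usually fall in the same calendar month. Setting a missing day to the 1st then nearly always puts the onset before first dose. A programmer who follows Appendix 2 as written would label such events pre-treatment and leave them out of the primary count. One who follows 6.4 would keep them. The plan supports both derivations, so the choice could be made after the data have been seen.

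**Working it through.** **1. The two rules on one record.** First dose 15JUN2021, last dose 24JUN2021 (Day 10), onset --JUN2021.

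| Rule | Step | Period |
|---|---|---|
| Appendix 2, then the 6.4 inequality | Onset set to 01JUN2021, before 15JUN2021 | Pre-treatment |
| SAP 6.4 default | Onset month equals first-dose month, so no contrary evidence | TEAE |

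The rules agree if first dose is on the 1st. They also agree if a true TEAE starts in the next calendar month, because the 1st of that month then lies inside the window.

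**2. How often they disagree for true TEAEs lacking only the day.** The plan gives no figure to reproduce here. Assumptions: first-dose dates evenly spread over a 365-day year, last dose on Day 10 (window Days 1 to 11), onset evenly spread over the window. For 6.4, only the recorded date parts are used as evidence.

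- Pairs of first-dose date and onset day: 365 × 11 = 4,015.
- Onset in the next month (rules agree): 12 × (0 + 1 + ... + 10) = 12 × 55 = 660.
- First dose on the 1st (rules agree): 12 × 11 = 132.
- Disagreement: 4,015 − 660 − 132 = 3,223, and 3,223 / 4,015 = 80.3%.

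The share depends on onset day: (365 − 12) / 365 = 96.7% on Day 1, falling to (365 − 120 − 12) / 365 = 63.8% on Day 11. If dosing ends on Day 11, it is (4,380 − 792 − 144) / 4,380 = 78.6%. Enumeration of all 1,095 first-dose dates in 2021 to 2023 also gives 80.3%. It gives 91.5% when only the month is missing and 98.4% when only the year is known.

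**3. Effect on the primary rate.** The planning rate is 37.9% of 310 (SAP 6.8), and 0.379 × 310 = 117.5 children. As a yardstick, 1.96 × √(0.379 × 0.621 / 310) = 5.40 points. That reproduces the plan's interval of 32.5% to 43.3% (the plan prints ±5.43). One child is 1/310 = 0.32 points. The documents do not say how many children would be affected, so the numbers moved below are assumptions.

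| Children whose only TEAE is moved | Rate | Exact 95% CI |
|---|---|---|
| 0 | 117/310 = 37.7% | 32.3 to 43.4 |
| 1 | 116/310 = 37.4% | 32.0 to 43.1 |
| 5 | 112/310 = 36.1% | 30.8 to 41.8 |
| 10 | 107/310 = 34.5% | 29.2 to 40.1 |

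**4. AEs that truly start after treatment.** For day-missing AEs with onset evenly spread over Days 12 to 28, the enumeration gives:

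| Rule | TEAE | Pre-treatment | Post-treatment |
|---|---|---|---|
| Appendix 2 | 36.2% | 34.2% | 29.6% |
| SAP 6.4, recorded date parts only | 70.4% | 0% | 29.6% |

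**The case against.** **The intent can be inferred.** SAP 6.4 contains the TEAE definition and speaks of partial dates. If Appendix 2 decided every partial date, that wording and its month-and-year example would have almost nothing to do. This stands as a guide to intent, and 6.4 is probably meant to govern. But Appendix 2 names AEs and gives period assignment as its purpose, so it cannot be read as a rule for listings only.

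**Other text limits the risk.** Protocol 8.3.1 sends non-serious occurrences between consent and first dose to medical history, so a pre-treatment label on such an AE record should look odd. SAP 6.4 also starts the pre-treatment period at the preliminary visit, and an imputed 1st of the month may precede that visit. Both points help detection, but neither ranks the rules. The Schedule of Activities footnote on AEs, Protocol 5.4.3.1 and SAP 16.1.1 describe AE collection or reporting from consent.

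**Partial dates should be few.** The Schedule of Activities says: "The parent/legal guardian should record the AEs, dosing information, diarrhoea related information in the Dairy Card". The card runs until the end-of-therapy visit, and AEs are asked about on Days 3 to 5, 12 to 14 and 22 to 28. The study is single-arm with no formal hypothesis. This stands, and it limits the size of the problem.

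**Two stronger readings fail.** A reader might infer that Appendix 2 can only lower the TEAE rate. That holds only if the recorded date parts are the sole evidence allowed under 6.4, whose month-and-year case is given as an example. Take first dose 28JUN, last dose 07JUL, no AE reported at the end-of-therapy visit (09 to 11JUL), and an AE dated --JUL first reported at follow-up (19 to 25JUL). Appendix 2 gives 01JUL, a TEAE. Under 6.4 the visit record is arguably contrary evidence, which makes the AE post-treatment. A reader might also infer that SAP 12 ranks 6.4 above Appendix 2 for medications. It only points to 6.4, and Appendix 2 still names concomitant medication.

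**Conclusion.** The inconsistency is real and reaches the primary endpoint. For an AE missing only the start day, with onset in the first-dose month and first dose not on the 1st, Appendix 2 gives pre-treatment and 6.4 gives TEAE. Following Appendix 2 therefore drops true TEAEs. Under the even-spread assumptions with last dose on Day 10, this happens to about 80% of true TEAEs that lack only the day.

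That percentage applies only to dates already partial; it is not a share of all TEAEs. The main effect is to lower the rate by 0.32 points per child whose only TEAE is moved. The total cannot be computed and is probably small against a half-width of about 5.4 points. The documents do not support a claim of material bias, or that the shift can go only one way. The point is still worth settling, because the primary flag should have one derivation, fixed in advance.

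**What to change.** Add to SAP Appendix 2 that:

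- SAP 6.4 decides the period of any AE with a missing or partial start date;
- an imputed date is not itself evidence against treatment emergence;
- other recorded evidence may be, such as the known date parts, the AE stop date and the visit at which the AE was first reported;
- imputed dates are used only where they are consistent with 6.4.

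A short exception for dates in SAP 7.3 would complete the change.

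The cost is this text and a check of the TEAE derivation program; no new data are needed. The downside is that the 6.4 default may count some post-treatment AEs with partial dates as TEAEs, so the reported rate may be slightly higher. The 70.4% in step 4 uses the recorded date parts alone; admitting the stop date and the visit of first report can only reduce it.
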